4.3 Measures to minimize bias

Different biases might arise in this project. To prevent selection bias and confounding in the two study arms, we will use stratified block randomization to balance the two arms with respect to important baseline characteristics. Due to the nature of the intervention, neither the participants, nor the data collectors of the study, nor the statistician can be blinded. However, to reduce

selective counting of CFUs on the hand-rinse samples, the lab workers assessing the number of CFUs will be blinded.

In Module 1, the RANAS and KAP survey, we expect a recall bias and a desirability bias. To minimize the recall bias, participants will not be asked to report any events which have taken place longer than a week ago with the exception of one question about their last training on handwashing. To reduce the desirability bias, the people administering the survey will not label themselves clearly as Tdh staff members, because local people know that Tdh often delivers humanitarian aid in the region and might want to impress the Tdh team. Additionally, to reduce any study personnel bias, the data collectors will all receive a training in advance. Their ID will be recorded in the survey form in order to be able to conduct quality control.

For Modules 1 to 3, data collectors have to upload the completed surveys every night, once they have a stable internet connection. All of the surveys will have the data collector's ID. The PhD student from Swiss TPH will control every second day how long the data collectors took to complete a survey, if certain answers are always the same for specific data collectors and the amount of missing data per survey. In addition, the GPS location of the tablet will be recorded to make sure that the data collection actually took place at the predefined location. These components will be correlated in the statistical software R (version 4.1.3) to test for significant differences between data collectors. In case a data collector delivers significantly different results which are not deemed realistic by the Swiss TPH study team and the local main correspondent of Tdh, the staff will be asked to comply to predefined rules once. If they still do not comply afterwards, they will be replaced. Faulty data from these staff members can then not be used any more for analysing the results of the h4h project. Modules 1-3 will be repeated two months after the intervention and nine months after the intervention. For Module 5, the proportion of reported health outcomes per year will be correlated with the health care facility four times during the survey year.

For Module 2, the handwashing observations, a Hawthorne effect is to be expected. Once the participants notice that they are being observed, they might change their behaviour accordingly. We will not be able to completely eliminate this bias. However, by not declaring that the observer is part of the h4h project, the participants will not know that the observer is focussing on handwashing behaviour. In scenario 1 of the observation technique, a bigger Hawthorne effect is expected, as people can ignore a camera more easily than an observer who constantly takes notes. However, we expect that with scenario 2 more handwashing opportunities or actions will not be clearly visible because the HCW or patient might obscure the view from the camera by their position in the room.

In Module 3, the microbiological analysis, a study personnel bias could influence the quality of the hand rinse samples and the accuracy of counting the CFUs. To be aware of differences between the data collectors, their ID will be stored during the sample collection on ODK. The number of CFUs per plate will be correlated with the people who collected the data to see if there are any significant differences between data collectors. The people counting the number of CFUs will be blinded and therefore do not know if the sample comes from the intervention or the control group. Additionally, every 10th sample will be duplicated during the data collection and the CFUs on every 10th plate will need to be counted additionally by another staff member as a quality control.

In Module 4, the reporting of pre-defined health outcomes, different biases might arise. Depending on how dutifully the HCWs report and on the severity of the outcomes, a detection bias might occur. We will test for this bias by correlating the health care facility with the proportion of reported outcomes over a year. In order to intervene in case such differences exist, we will correlate the data in each quarter of the study year as a form of quality control. In addition, a form of selection bias can happen if a certain group of patients does not report back after suffering any form of infection they contracted at the health care facility. For example, if neonatal sepsis occurs, patients might directly go to a tertiary health care facility instead of a PHCF. We are aware that this module is suboptimal due to a rather small sample size and a lack in possibilities of patient-follow up.

However, this is only part of an exploratory objective. We still think that if differences can be observed between the two intervention arms, this module is of high importance as it would demonstrate the significance of good hand hygiene in PHCFs. If these differences can be demonstrated on a local level, motivating local HCWs for future handwashing interventions might become easier.

To assure the quality and functioning of the Gravit'eau handwashing stations, regular integrity tests and water quality tests will show if the systems are still functional and capable to remove the bacteria. *E.coli* tests of handwashing water will show if there is any recontamination or any integrity problem. In case there is a problem, we will provide an alternative solution (e.g. bucket with soap) and rehabilitate the handwashing systems or dose chlorine into handwashing systems and repeat the test.

In case a facility has 25% higher negative health outcomes than the average of all facilities, the regional Ministry of Health will be consulted to check if this is usual. If not, the study will have to be stopped in this facility.

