4 STUDY DESIGN

The overall project will follow an multi-center cluster-randomized controlled trial (cRCT) design (Figure 3). Prior to this study, the Facility and Evaluation Tool for WASH in Institutions (FACET)

has been used to assess the WASH infrastructure of the PHCFs in the study regions. From these PHCFs a subsample was identified which fulfils certain inclusion criteria (for the inclusion criteria see chapter 5.2 Inclusion criteria).

This subsample was handed over to the local Tdh collaborators who carefully assessed the security situation around the facilities. The Tdh collaborators then chose 24 facilities which are most probable to still be accessible for data collection within the next year. These 24 PHCFs will then be distributed into two arms (intervention vs. control) with stratified randomization using computer-generated randomization code provided by an statistician not involved in any field activities. The intervention arm will receive the full intervention package (handwashing station, behavioural change intervention, capacity development, management support, chlorination training and WASH FIT). The control arm will receive nothing for the duration of the intervention (9 months). Afterwards they will receive the same intervention package with potential improvements identified in the former intervention group.

In the chosen PHCFs all HCWs present at the day of data collection who fulfil the inclusion criteria will be asked to participate in the study. We aim to have as many of the HCWs in all of the Modules 1 and 3 as possible. For Module 2, only a maximum of 10 HCWs per facility will be observed.

[figure not shown]

Figure 3: Consort flow diagram of the PHCF selection for the h4h cRCT in Mali

The methods to achieve the different objectives of this project are summarized in Table 2. These modules will include qualitative and quantitative data approaches in order to enable a triangulation of the overall project results. The following modules will be used in the cRCT and the overall project: (i) Module 1: Combined RANAS and KAP survey, (ii) Module 2: Structured handwashing observations, (iii) Module 3: Microbiological analysis of hand rinse samples, (iv) Module 4: Diary approach for pre-defined health outcomes, (v) Module 5: Focus Group Discussions (FGDs) and (vi) Module 6: Key informant interviews (KIIs).

Table 2: Overview of different project modules and analysis by objective

Module	Objective	Analysis

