7.3 Confidentiality and coding

Project data will be handled with uttermost discretion and is only accessible to authorized personnel who require the data to fulfil their duties within the scope of the research project. On the CRFs and other project specific documents, participants are only identified by a unique participant number (ID). The CRFs contain the ID assigned to the participant by the field staff. The name of the participant will be kept in a separate confidential enrolment log that matches identifying codes with the participants' names and residencies during the study. This will only be accessible by the local study coordinator and the people conducting the survey. The document will be stored in the locked cabinet on site and destroyed after the end survey in order to completely anonymize participants.

Biological material (the hand rinse samples) in this project is not identified by participant name but by a unique participant ID. Biological material is appropriately stored in a restricted area only accessible to authorized personnel for a maximum of 48h to be analysed.

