9.4 Participant confidentiality

The Investigators must ensure that the participant's confidentiality will be maintained. HCWs will be identified on the Case Report Forms with a unique participant ID composed of initials of the study country, a number of the health care facility, and a letter from a to z (e.g. BF-01-a). Patients of the HCWs will not be identified, only their gender and age group will be recorded. The Investigators will keep a separate confidential enrolment log that matches identifying codes with the participants' names and residencies.

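### The laboratory blind for colony counting is not secured: the sample ID contains the facility number, and facilities are what is randomised

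*Combined protocol and SAP*

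**What the plan says.** Section 4.3 accepts that participants, data collectors and the statistician cannot be blinded. It makes one exception, to limit selective counting of colonies: "the lab workers assessing the number of CFUs will be blinded". Later in the same section, on telling the two arms apart in Module 3, it adds: "The people counting the number of CFUs will be blinded and therefore do not know if the sample comes from the intervention". As quality control, every tenth sample is duplicated and every tenth plate is counted by a second person.

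The labelling rule is in section 7.3: "Biological material (the hand rinse samples) in this project is not identified by participant name but by a unique participant ID". Section 9.4 describes that identifier as a "unique participant ID composed of initials of the study country, a number of the health care facility, and a letter from a to z", with BF-01-a as the example.

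Section 4 sets the unit of allocation: "These 24 PHCFs will then be distributed into two arms (intervention vs. control) with stratified randomization". On the contrast between arms it says: "The control arm will receive nothing for the duration of the intervention (9 months" in length), while the intervention arm gets the full package, including handwashing stations.

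Section 4 (Module 3) has samples processed in a field laboratory within four hours. Section 2.3 gives the implementing NGO's local teams a supporting role in both the intervention and all the data collection. Section 8.4 has the plates photographed and the pictures stored.

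**The concern.** The stated labelling rule works against the stated blind. The plan names a purpose for blinding the counters but no mechanism that would deliver it, and the one identifier it assigns to the samples carries the cluster number.

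This matters because CFU per hand (section 4.2, endpoint B) is the only outcome for which the plan claims blinded assessment. It stands beside openly unblinded observation, self-report and diaries kept by facility staff, so a reader would look to it for corroboration. Counting leaves room for judgement: section 4 sets the upper limit at 500 CFU per plate and requires both E. coli and total coliforms to be counted. If a counter knew the arm, expectation could influence the counts.

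**Working it through.** The plan gives no figure to reproduce. The check traces the label to the arm and then sizes the exposure.

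**From label to arm**

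1. Does the sample label identify the facility? Yes. Section 7.3 puts the participant ID on the sample, and section 9.4 puts the facility number in the ID.
2. Does the facility fix the arm? Yes. Section 4 randomises facilities, so all samples sharing a facility number belong to one arm.
3. Does the label alone show the arm? No. BF-01-a gives country, facility and worker. The reader must also know how that facility was allocated.
4. Is anything described that keeps this knowledge from the counters? No. No laboratory code, relabelling step, masking of the facility part of the ID or restriction on counters' access to the allocation appears in sections 4, 4.3, 7.3 or 8.4. The recount and the duplicates in 4.3 have no labelling rule of their own.
5. Could the allocation become known locally? Plausibly. The package is conspicuous at a facility, there are few facilities (24 in section 4; 24 per country in the synopsis), processing is in the field, and one organisation's teams support both delivery and data collection. This is opportunity, not evidence that counters know.

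**Exposure**

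Inputs: a mean of six staff per facility, range two to nine (section 6.2); both hands sampled (section 4, Module 3); three rounds, of which two follow the start of the intervention (synopsis, section 4.3).

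- Samples per facility per round: 6 × 2 = 12.
- Samples per facility after baseline: 6 × 2 × 2 = 24.
- Over the planning range of staff: 2 × 2 × 2 = 8 to 9 × 2 × 2 = 36.

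Duplicates are not counted. The baseline round is left out because it precedes delivery of the package. These figures assume that every worker takes part at each round. They show how many samples share one code, and so how many are exposed if that facility's arm becomes known. They do not measure bias.

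**Illustration of a shift (assumed)**

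The documents give no basis for the size of a counting bias. If counts in one arm were consistently 10% to 20% too low, the arm mean of log10 CFU would move by log10(0.9) = −0.046 to log10(0.8) = −0.097. The plan states no standard deviation or expected difference for this endpoint, so the shift cannot be judged against either.

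**The case against.** A reader might infer that the blind cannot hold and that a report claiming it would be untrue. The documents do not support that. The code does not show the arm, and nothing gives the counters the allocation. The randomisation code comes from a statistician outside the fieldwork. Section 4.3 treats laboratory workers separately from the unblinded data collectors, and no passage says that those who deliver the package also count plates. A counter without knowledge of the allocation could see BF-01-a and remain blind.

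It is also tempting to say that a counter can recognise the duplicates. How duplicates and recounted plates are labelled is not specified, so the most one can say is that nothing prevents it.

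Further points in the plan's favour: section 7.3 is about confidentiality and is not a laboratory procedure; section 4.5 says the modules will be piloted and adapted; the photographs in section 8.4 would allow a masked re-reading; the endpoint is secondary; and section 6.1.2 states no hypothesis about CFU.

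These points limit the claim and its importance. They do not remove it. Section 7.3 is the only labelling rule for these samples, and it conflicts with the purpose stated in 4.3. The photographs help only if they are coded and read without the facility number, which the plan does not require.

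**Conclusion.** The laboratory blind is claimed but not secured. Samples are identified by an ID that contains the facility number, that number gives the arm to anyone who knows the facility's allocation, and no re-coding or separation of counters from the allocation is described. Whether any counter would in fact know the arm cannot be settled from the documents, so the blinding claim is unsupported rather than shown to be false.

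The scope is secondary endpoint B at the two post-baseline rounds, about 24 samples per facility on the assumption of six workers giving both hands. The size and direction of any counting bias are unknown, and the 0.05 to 0.10 log10 shift is only an illustration. The primary endpoint, observed handwashing, is unaffected. The plan should be changed because the remedy is simple and this is its only claimed blinded assessment.

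**What to change.** In sections 7.3 and 4.3:

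- Label bags and plates with a random sample code that carries no country, facility or worker information. Give duplicates their own codes, and present recounted plates to the second reader under the random code only.
- Hold the link between sample code and participant ID in the ODK record, closed to counters.
- Record counts and plate photographs against the sample code, and merge with participant data only after counting is complete.
- State that counters have no access to the allocation. The code alone does not achieve this, because samples processed within hours of collection may arrive in facility batches.

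The cost is pre-printed labels and one scan field in the existing electronic form. The downside is a small risk of linkage error, which scanning the labels instead of typing the codes keeps under control.

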The Whirl-Pak bags containing the samples will be kept on ice in an isolation box and processed within 4 hours of sampling (45). Membrane filtration will be used to detect colony-forming units (CFUs) of *E. Coli* and total coliforms. In a field laboratory, the content of the bags will be passed through a 47-mm-diameter 0.45 µm cellulose filter. The filter paper will then be placed on growth media and incubated at 35°C ± 0.5°C for a duration of 24 hours for *E. Coli* and total coliforms (45). We plan to filter 100 mL per bag to detect CFUs of *E. Coli* and total coliforms. The exact amount of mL will be established during piloting as the volume used is dependent on the degree of bacterial contamination on the hands. Compact dry plates will be used for the detection of *E. coli* and total coliforms.

The lower detection limit of CFUs will be calculated by dividing 1 CFU/plate by the filtrate volume and then multiplying it with the total Whirl-Pak volume of 350 mL. The upper detection limit will be calculated by dividing 500 CFUs/plate by the filtrate volume and then multiplying it with the Whirl-Pak volume. For the statistical analysis, the CFUs per hand will be normalized and \log_{10} transformed (45).

Module 4: Diary approach for pre-defined health outcomes: Longitudinal data on hygiene-related health outcomes of patients and disease-related absences of HCWs will be collected during

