4.2 Secondary endpoints

The most important secondary endpoints in the survey are:

- A) Self reported handwashing practice to answer for each critical moment on a Likert scale ranging from almost never to almost always.
- B) The log-transformed number of total coliforms and E.coli CFUs per hand before handwashing.
- C) Hygiene-related health outcomes which are summarized in table 3. The sum of each outcome variable separately per facility will be used as a measure for statistical analysis. The health outcomes will be reassessed with local experts of the respective countries to assure feasibility before the start of the intervention.

Table 3: Hygiene-related health outcome variables for Module 4.

Outcome variable	Details
Absenteeism of health care worker	
 • Record of the event • Number of days absent • Reason for absence
Maternal mortality	
 • Record of the event • If known, reason of passing
Neonatal mortality	
 • Record of the event • If known, reason of passing
Neonatal sepsis(49)	
 • Record of the event • Number of days treated • Outcome (healthy, unknown, death)
Umbilical cord infection	
 • Record of the event • Number of days treated • Type of infection • Outcome (healthy, unknown, death)
Wound infection after stitching of surgical procedures	
 • Record of the event • Number of days treated • Outcome

Covariates were assessed with a directed acyclic graph (DAG) with RANAS variables as exposure variables and good handwashing practice as outcome variable (Appendix). Covariates for estimating the total effect of RANAS on good handwashing practice are age, education, sex, socio-economic status, previous training in hygiene, handwashing practices, position in the health care facility, and the water infrastructure of the health care facilities.

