4.6 Withdrawal and discontinuation

Participants may stop their participation at any time and withdraw their consent. Local staff is recruited and employed by Tdh and has to follow the terms and conditions of the local Tdh offices which are written in their work contract.

The overall h4h project or specific project sites can be discontinued due to several reasons by the project leader, such as:

- Ethical concerns (e.g. non-acceptance of proposed technical solutions)
- Insufficient participant recruitment
- Natural hazards (e.g. heavy floods, earthquakes)
- Damage and vandalism of infrastructure, technical failure of interventions
- Alternative interventions and projects at the same facilities not coordinated with us
- Limited access by Tdh staff due to any reason out of their control including pandemics, natural hazards or deterioration of security situation
- Political constraints restricting access to the health care facilities or the project implementation

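### The facility stop trigger is benchmarked on both arms together and its flags are never read by arm, so a harm shared by the intervention arm is diluted

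*Combined protocol and SAP*

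**What the plan says.** Section 4.3 (Measures to minimize bias) contains the only rule that acts on health outcomes: "In case a facility has 25% higher negative health outcomes than the average of all facilities, the regional Ministry of Health will be consulted". If the Ministry finds the level unusual, the study stops in that facility. No action at the level of the arm or the trial is stated.

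The same section plans a periodic look at the diary data: "we will correlate the data in each quarter of the study year as a form of quality control". It relates reports to facility, to find uneven reporting; arm is not mentioned. Section 6.3.1.1 has a model for the intervention effect on diary outcomes, but with no safety action attached. Section 4.6 gives wide discretion: "The overall h4h project or specific project sites can be discontinued due to several reasons by the project leader, such as". None of the examples that follow is a health-outcome signal.

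Sections 4 and 4.4 give 24 facilities, 12 of them intervention; the Synopsis gives 24 per country and 48 in total. Section 4.2 uses the sum of each outcome per facility and states no denominator. Its Table 3 also lists "Absenteeism of health care worker" among the hygiene-related health outcomes.

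**The concern.** The package goes to every intervention facility, so any harm from it would tend to be shared across that arm. A rule that looks for one facility standing out from the rest suits a local problem. For a shared problem it is weak, because half of the comparison group carries the same excess.

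The useful signal would then be the division of flags between arms, and nobody is asked to look at it. The Ministry is consulted one facility at a time, and several separate consultations need not add up to a question about the package.

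Two terms are also open. The group being averaged could be one country or both. And section 4.3 does not say whether staff absences count as negative health outcomes.

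**Working it through.** The plan gives no derivation for the 25% threshold, so there is no figure to reproduce. The check is what the rule does under a shared harm.

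**Expected rates.** Let the control rate be 1 and the rate in every intervention facility be r. With equal arms:

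- all-facility average = (1 + r)/2
- intervention facility relative to that average = 2r/(1 + r)
- at r = 1.25: 2.50/2.25 = 1.11
- at r = 1.4: 2.8/2.4 = 1.17
- at r = 1.5: 3.0/2.5 = 1.20
- trigger met when 2r/(1 + r) = 1.25, so 0.75r = 1.25 and r = 1.67

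Against the control average the ratio is r itself, so the trigger is met at r = 1.25. Leaving the facility out of its own average changes little: with 12 + 12 facilities, r = 1.25 × 12/(23 − 1.25 × 11) = 15/9.25 = 1.62; with 24 + 24, r = 30/18.25 = 1.64.

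**Flags with chance variation.** The documents give no event rates, so event means, the coefficient of variation (CV) and r = 1.4 are assumptions. Counts were simulated as Poisson with gamma variation between facilities: CV 0.3, 12 v 12 facilities, 20,000 runs. A flag is a count above 1.25 times the mean of all 24. Entries are expected numbers of facilities.

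| Mean events per control facility | r | Intervention flags | Control flags | Total of 24 | Intervention facilities above 1.25 × control average (of 12) |
|---|---|---|---|---|---|
| 20 | 1.0 | 2.8 | 2.8 | 5.5 | 3.0 |
| 20 | 1.4 | 4.6 | 1.2 | 5.8 | 7.0 |
| 5 | 1.0 | 3.5 | 3.5 | 7.0 | 3.6 |
| 5 | 1.4 | 4.8 | 2.0 | 6.8 | 6.5 |
| 2 | 1.0 | 3.9 | 3.9 | 7.8 | 4.1 |
| 2 | 1.4 | 4.9 | 2.8 | 7.7 | 6.2 |

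In these settings the total hardly moves, while the split does. This depends on the CV: at CV 0.15 and a mean of 100 events, the total rises from 2.0 to 3.9.

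**Why the comparison should stay within country.** Table 1 gives median busiest-month outpatients of 365 in Mali and 470 or 651 in the two Burkina Faso pilot samples. If counts followed outpatient volume (an assumption), a typical Burkina Faso facility would sit at 470/417.5 = 1.13 or 651/508 = 1.28 of a two-country average with no harm at all. If counts followed births (medians 19, 17 and 18), the difference would be small.

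**The case against.** The strongest reply is that the present rule would still react. In the first setting above, 4.6 of 12 intervention facilities are flagged at r = 1.4. Each flag sends the Ministry to judge what is usual, a standard that does not depend on the pooled average. Unblinded staff might notice the pattern, and section 4.6 lets the project leader stop the project. Station integrity and water tests, with corrective action, address the recycled-water hazard directly. All of this stands. What remains is that none of these safeguards has a by-arm criterion and the water tests do not use patient outcomes.

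The second reply is about the data. Section 4.3 itself warns: "Depending on how dutifully the HCWs report and on the severity of the outcomes, a detection bias might occur". It also calls this module suboptimal and exploratory. Section 9.2 expects that better hygiene may attract patients, so event counts could rise in the intervention arm with no change in risk per patient. Diaries start only after the intervention, so there is no diary baseline to separate these effects. This stands too, and it limits the remedy.

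A reader might infer that the plan needs a formal by-arm alert. The material does not support one on raw counts. Take a one-sided 10% t-test on square-root cumulative counts, three quarterly looks, CV 0.3 and 1 to 5 events per facility-quarter. If intervention counts are 20% higher through volume or fuller reporting alone, at least one alert occurs in 38–53% of trials with one country and 48–70% with both pooled. Further looks raise this, and checking diary completeness would not reveal extra patients.

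**Conclusion.** The point holds as a minor weakness of the safety rule. A harm common to the intervention arm must reach a rate ratio of 1.67, not 1.25, before an intervention facility meets the trigger on expected rates, and no rule reads the flags by arm. The 1.67 rests only on equal arms and a uniform effect. The flag counts rest on assumed event rates and variation.

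Three stronger inferences are tempting and are not supported:

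- That the trigger cannot detect harm from the package. It can: flags move towards the intervention arm, and the Ministry's judgement is independent of the average.
- That the total number of flags is always uninformative. This depends on between-facility variation; the split by arm is simply the more informative signal.
- That harm is likely. The Synopsis puts the study in risk category A, and the documents give no sign of harm.

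**What to change.** In section 4.3, add a few sentences to the existing quarterly diary review:

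1. Tabulate the flags by arm, and compare each intervention facility with the control-facility average in the same country.
2. Show infection and death events alongside births or visits from facility registers where available, and the diary sheets received by arm.
3. If flags cluster in the intervention arm, check reporting completeness and patient volume first. If the imbalance remains, the project leader and the regional Ministry review the package across all intervention facilities.
4. Keep the table descriptive, with no formal test on raw counts.
5. State that staff absences do not count in the trigger, and whether the average in the existing rule covers one country or both.

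The cost is one table per quarter from diaries already collected monthly (section 7.1), plus register counts where they exist. There are three downsides. Uneven reporting or higher volume may cause false concern, and a count of sheets does not show events left off a sheet. Sensitivity is low when events are rare, so a quiet table is not proof of safety. Finally, section 4.3 says that "neither the participants, nor the data collectors of the study, nor the statistician can be blinded", but knowing the allocation is not the same as seeing accumulating results by arm. The table should therefore go only to those responsible for safety, and not to the observers of the primary endpoint.
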